9.5 Sex and Ethnicity

Based on previous data from E1608, E2603 the anticipated accrual in subgroups defined by sex and race is:

Ethnic Category	Sex		
	Females	Males	Total
Hispanic or Latino	0	1	1
Not Hispanic or Latino	106	193	299
Ethnic Category: Total of all subjects	106	194	300

Racial Category			
American Indian or Alaskan Native	0	0	0
Asian	0	0	0
Black or African American	3	0	3
Native Hawaiian or other Pacific Islander	0	0	0
White	103	194	297
Racial Category: Total of all subjects	106	194	300

The accrual targets in individual cells are not large enough for definitive treatment comparisons to be made within these subgroups. Therefore, overall accrual to the study will not be extended to meet individual subgroup accrual targets.

9.6 Study Monitoring

This study will be monitored by the ECOG-ACRIN Data Safety Monitoring Committee (DSMC). The DSMC meets twice each year. For each meeting, all monitored studies are reviewed for safety and progress toward completion. When appropriate, the DSMC will also review interim analyses of outcome data. Copies of the toxicity reports prepared for the DSMC meetings are included in the study reports prepared for the ECOG-ACRIN group meeting (except that for double blind studies, the DSMC may review unblinded toxicity data, while only pooled or blinded data will be made public). These group meeting reports are made available to the local investigators, who may provide them to their IRBs. Only the study statistician and the DSMC members will have access to interim analyses of outcome data. Prior to completion of this study, any use of outcome data will require approval of the DSMC. Any DSMC recommendations for changes to this study will be circulated to the local investigators in the form of addenda to this protocol document. A complete copy of the ECOG-ACRIN DSMC Policy can be obtained from the ECOG-ACRIN Operations Office – Boston.

9.7 Correlative Objectives

Genetic associations with irAE status will be assessed using Fisher's exact test, one-degree-of-freedom genotypic trend test (analogous to the Cochran-Armitage test) or the two-degrees-of-freedom chi-squared test of independence at each individual SNP marker. Tests of association will be adjusted for age, sex, center or clinical protocol, and dose as well as AJCC stage, ulceration, performance status, lactase dehydrogenase (LDH) level, number of involved sites, using

logistic regression modeling assuming an additive genetic model. Within distinct genetic pathways or regions, P-values of individual SNP marker associations will be adjusted for multiple testing by controlling the false discovery rate (FDR).

Analysis for survival outcomes will occur within the framework of Cox proportional hazards, although otherwise similar to analyses described above for irAEs. In addition to adjusting for age at diagnosis, sex, center, clinical trial and dose, adjustment for variables potentially associated with prognosis including AJCC stage, ulceration, performance status, lactate dehydrogenase (LDH) level, number of involved sites, will also be made.

For replication phase irAE outcomes, the study has 80% power to detect a per-allele RR of 2.90 or greater for SNP markers with a MAF of at least 0.10. For analysis of 2 year survival, the study has 80% power to detect a per-allele HR of 1.83 or greater for SNP markers with a MAF of at least 0.10. These detectable measures of effect compare favorably to point estimates we found in our small preliminary study.

9.8 Patient Reported Outcomes (PROs) Objectives

All enrolled patients will participate in the PROs component of the study. Only those who receive at least one dose of protocol treatment (i.e., all treated patients) will be included in the PROs analysis.

Several objectives are proposed in the patient-reported outcomes (PROs) assessment study: (a) to compare quality-adjusted time without symptoms or toxicity at 2 years between initial treatments (i.e., arm A: ipilimumab + nivolumab (with subsequent dabrafenib + trametinib) vs. arm B: dabrafenib + trametinib (with subsequent ipilimumab + nivolumab)); (b) to compare overall function between initial treatment (i.e., arm A: ipilimumab- + nivolumab (with subsequent dabrafenib + trametinib) vs. arm B: dabrafenib + trametinib (with subsequent ipilimumab- + nivolumab) at baseline, weeks 6, 12, months 6, 12, 18, and 24 from study entry); and (c) to assess function and patient-reported symptoms by treatment sequence for ipilimumab +nivolumab (arm A vs. D), and dabrafenib + trametinib, (arm B vs. C) at baseline, 6-, 12-weeks, and 6-months after the initiation of treatment in each step.

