4.4 Instructions for Patients who Do Not Start Assigned Protocol Treatment

If a patient does not receive any assigned protocol treatment, baseline and follow-up data will still be collected and must be submitted through Medidata Rave and EASEE-PRO according to the schedule in the EA6134 Forms Completion Guidelines.

5. Treatment Plan

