initial treatment (in step 1). For patients with severe toxicities reported in step 1 but no end date reported, TOX1 will be capped at the date of disease progression in step 1 or death without progression. TOX2 is defined as the number of days with grade 3 or 4 toxicities reported after the first disease progression on the initial treatment (in step 1) and prior to the second disease progression on the subsequent treatment (in step 2). For patients with severe toxicities reported during this period but no end date reported, TOX2 will be capped at the date of disease progression on the subsequent treatment or death without progression. For patients not receiving the subsequent treatment, TOX2 is counted as 0.

There are a couple of special notes for this expanded Q-TWiST analysis. If patients die during an early state and EQ-5D is not administered thereafter, the utility score in each of subsequent states will be defined as 0. If patients withdraw or lost to follow-up during an earlier state, the utility score in subsequent states will be assigned 0.. Finally, since Q-TWiST is being computed for 2 years in this study, once the duration of earlier states reach 2 years, the utility score collected in subsequent states will be used for these patients in the 2-year Q-TWiST analysis.

The mean amount of time for each health state and the average group utility scores will be summarized by initial treatment (i.e., arm A: ipilimumab + nivolumab (with subsequent dabrafenib + trametinib) vs. arm B: dabrafenib + trametinib (with subsequent ipilimumab + nivolumab)). The Q-TWiST subscore and the overall Q-TWiST score will then be reported by initial treatment. Differences between treatment groups in the mean Q-TWiST score (including the overall score and the subscore) will be calculated. For each score, a 95% confidence interval (CI) and two-sided P-value for testing the null hypothesis of no difference between treatment groups will be conducted using a Z-test (with normal approximation), with standard errors calculated by the bootstrap method. The bootstrap will be performed by repeated sampling, with replacement, from the sample of patients enrolled in this study, to obtain a new sample. The means for the new sample will be calculated using the same method as described above. This process will be repeated 1000 times. Based on the means obtained by the bootstrap method, the standard errors can be calculated.

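### The primary patient-reported comparison (Q-TWiST, Arm A vs Arm B) leaves out randomised patients who never start treatment; it should use all randomised patients by assigned arm

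*Combined protocol and SAP*

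**What the plan says.** Section 9.8 opens with "All enrolled patients will participate in the PROs component of the study" and then narrows the analysis: "Only those who receive at least one dose of protocol treatment (i.e., all treated patients) will be included in the PROs analysis". The restriction applies to all the objectives listed there, the first of which is the Q-TWiST comparison of Arm A with Arm B.

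Other sections bear on it:

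- Section 1.9 describes the primary patient-reported comparison as one between initially assigned treatments over 2 years. Section 2.4.1 compares the initial arms, taking overall survival (OS) into account.
- Sections 9.8.1 and 9.8.2 build Q-TWiST from overall survival, split into five health states. PFS1, PFS2 and OS all start at study entry. Utilities enter as one average weight per state and arm, computed from patients with data.
- Section 9.4 analyses the 2-year OS rate, OS and the 3-year OS rate by intention to treat.
- Section 4.4 says that for patients who receive none of their assigned treatment, "baseline and follow-up data will still be collected".
- Section 5.9.1 schedules long-term patient-reported assessments only for patients who had a dose and no non-protocol therapy.

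For inference, section 9.8.2 says that the interval and P-value "will be conducted using a Z-test (with normal approximation), with standard errors calculated by the bootstrap method". It continues: "The bootstrap will be performed by repeated sampling, with replacement, from the sample of patients enrolled in this study, to obtain a new sample". Then: "The means for the new sample will be calculated using the same method as described above". And: "This process will be repeated 1000 times". It gives no all-randomised sensitivity analysis for Q-TWiST and does not say whether resampling is done within arm.

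**The concern.** A treated-only set is common for symptom scores, because someone who never took the drug has no treatment symptoms to report. That reason does not carry over to Q-TWiST, which is survival time with quality weights. Its clock starts at study entry, but membership of the analysis set depends on a later event.

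Whether a patient starts can depend on the arm. No blinding is described, the arms are infusion against oral treatment, and section 5.1 allows up to 7 working days between randomisation and first dose. A patient who refuses the assignment or deteriorates in that interval disappears from the arm to which he or she was allocated.

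At stake is whether the Q-TWiST difference is a comparison of the randomised groups. The OS component inside it would also rest on a different set of patients from the reported OS result, although section 1.1 presents these outcomes as a complement to OS.

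**Working it through.** **1. The plan's own figure.** Section 9.8.1 takes the clinically important difference (CID) as 10% of median survival in the control group. With 50% alive at 24 months the median is 24 months, so CID = 0.10 × 24 = 2.4 months. For n = 135 per group, SD 7 and two-sided alpha 0.05:

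power = Φ(2.4 / (7 × √(2/135)) − 1.96) = Φ(2.817 − 1.96) = 80.4% (80.1% by the exact t-test).

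The plan states 80%. All 12 rows of its table reproduce within 2 points. The table is sound and does not depend on this point.

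**2. Shift from dropping non-starters.** In one arm let u be the share who never start and D the mean deficit of non-starters against starters, in months. The all-randomised mean is the treated mean minus uD, so the treated-only mean is too high by uD. For the A − B difference:

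shift (treated-only minus all-randomised) = uA × DA − uB × DB.

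The documents give neither u nor D, so every value below is an assumption. With the same D in both arms:

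| uA, uB | D = 3 | D = 6 | D = 12 |
|---|---|---|---|
| 1%, 1% or 3%, 3% | 0 | 0 | 0 |
| 1%, 3% | −0.06 | −0.12 | −0.24 |
| 2%, 5% | −0.09 | −0.18 | −0.36 |
| 0%, 5% | −0.15 | −0.30 | −0.60 |

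The signs reverse if Arm A has the larger share. Equal shares do not remove the shift if prognosis differs: with 3% in each arm, DA = 12 and DB = 3, it is 0.36 − 0.09 = 0.27.

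As a further illustration, take exponential survival with the planned 70% and 50% at 24 months. The 24-month restricted means are 20.2 and 17.3 months. If non-starters average 12 months (assumed), the deficits are 8.2 and 5.3. With 5% against 1% non-starters the shift is 0.05 × 8.2 − 0.01 × 5.3 = 0.41 − 0.05 = 0.36 month. With 3% against 1% it is 0.25 − 0.05, about 0.2 month.

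The largest value, 0.60, is 25% of the CID (0.60 / 2.4). These are survival months. Q-TWiST multiplies them by utilities, so at an assumed utility of 0.8 they become 0.48 for the largest case and 0.29 for the 0.36 case.

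**3. Precision.** Holding the difference and SD fixed, the exact t-test power is 84.1% with 150 per arm at SD 7 and 82.1% with 142 (about 5% untreated). At SD 10 the figures are 54.5% and 52.2%. On these terms, keeping everyone costs no power.

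**4. Bootstrap wording.** A simulation with 150 per arm, SD 7, a 2.4-month difference, one normal score per patient, 1000 resamples and 40 trials per row compared three readings. Standard errors are shown relative to resampling treated patients only:

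| u (both arms), D | resample enrolled, then keep treated | resample enrolled, no restriction |
|---|---|---|
| 1%, 6 | 1.002 | 1.004 |
| 3%, 6 | 1.004 | 0.997 |
| 5%, 6 | 1.004 | 0.998 |
| 5%, 12 | 0.998 | 1.038 |
| 10%, 12 | 1.007 | 1.057 |

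**The case against.** **The set matches the data collection.** Section 5.9.1 schedules long-term EQ-5D only for dosed patients, so a treated-only set is coherent with what is collected. This stands for the utilities. It does not stand for the durations: section 4.4 keeps follow-up on non-starters, and because weights are arm averages over patients with data, a non-starter can contribute survival time without an EQ-5D of his or her own.

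**Including non-starters is not trivial.** PFS1 and TOX1 are defined by progression on the initial treatment, which a never-treated patient does not have. Section 9.8.2 also sets later utilities to 0 after withdrawal or loss to follow-up. This stands, and explicit rules are needed.

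**The effect may be negligible.** Performance status 0 or 1 and a 7-working-day window limit early deterioration, and nothing in the documents shows that non-starters are more frequent or worse off in either arm. This also stands. Size and direction are unknown.

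**A late change can look post hoc.** The protocol has already been amended on monitoring committee advice. That is a reason to date the change and to report both analyses.

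**Stronger readings to avoid.** A reader might infer from the word enrolled that the standard error belongs to a different population from the estimate. The documents do not support that. The next sentence, "The means for the new sample will be calculated using the same method as described above", can be read as applying the treated-only rule inside each resample. That gives a valid standard error (ratios 0.998 to 1.007). Even with no restriction it changes by only about 0% to 6% in the scenarios tried. A reader might also take 0.36 month, 15% of the CID, as an estimate of the bias. It is an illustration on assumed rates and in unweighted survival months.

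**Conclusion.** The concern holds for the analysis set. The plan builds a post-randomisation exclusion into a survival-based comparison of randomised arms, and data already being collected would let it be avoided. It can bias the Q-TWiST difference if non-start shares or the prognosis of non-starters differ between arms, and not otherwise. On assumed shares of 0% to 5% and deficits of 3 to 12 months, the shift is about 0 to 0.6 survival months in either direction, less after utility weighting, against a CID of 2.4 months.

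The bootstrap text is ambiguous about its sampling frame, but no standard-error fault is shown. Q-TWiST is primary only among the patient-reported objectives, which section 2.4 lists as secondary for the trial, so the 2-year OS conclusion and the power table are unaffected. The change is worth making because it removes an avoidable source of bias at little cost.

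**What to change.** In sections 9.8 and 9.8.2:

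1. Define the Q-TWiST set as all randomised patients by assigned arm, with OS and PFS1 from randomisation.
2. For never-treated patients, set TOX1 and TOX2 to 0. Count any documented progression or death as the PFS1 event. For PFS2 use the rule already given for patients who do not enter step 2. Apply arm-average utilities.
3. State how item 2 fits with the zero-utility rule for withdrawal and loss to follow-up.
4. Keep the treated-only analysis as a sensitivity analysis and report non-starters by arm.
5. State that the bootstrap resamples the Q-TWiST analysis set within arm.

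PROMIS and PRO-CTCAE analyses may stay in treated patients. Date the change. If Q-TWiST results by arm have already been seen, say so and show both analyses side by side.

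The cost is plan wording and a few conventions, with no new data collection. The downside is that arm-average utilities, measured largely under treatment, are applied to a few patients with no on-treatment EQ-5D.

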9.8.1 Statistical consideration for PROs

The primary objective is to compare the overall clinical benefit between initial treatments (i.e., arm A: ipilimumab + nivolumab (with subsequent dabrafenib + trametinib) vs. arm B: dabrafenib + trametinib (with subsequent ipilimumab + nivolumab)), accounting for toxicities and overall survival. The quality-adjusted time without symptoms of disease progression or toxicity of treatment (Q-TWiST) analysis will be used to provide an integrated measure of quality and quantity of survival time. The Q-TWiST score based on overall survival at 2 years will be computed and compared, with the details of the Q-TWiST score described in the following section. A clinically important difference (CID) in the Q-TWiST score is recommended to be 10% of median survival in the control group.⁴⁴ It is hypothesized in this trial that the 2-year OS rate is 70% for Arm A and 50% for Arm B, the CID for Q-TWiST is thus estimated to be 2.4 months in this study for the Q-TWiST power calculations. A standard deviation of 4.0 was

estimated based on the difference of 1.5 months, together with its 95% confidence interval of (-6.3, 9.3), in the duration of the TWiST state between high-risk melanoma patients receiving IFN α 2b and those on observation.⁴⁵ The table below lists the power, using an independent-sample t-test with a two-sided type I error of 0.05, based on various projected standard deviation in the Q-TWiST score assuming different number of patients in each comparison arm. As shown in the table, with 135 patients in each group (as proposed for the 2-year OS primary endpoint), we have 80% power to detect a CID of 2.4 months in the Q-TWiST score with a standard deviation of 7 in the Q-TWiST score. The power drops to 50% with 135 patients in one group and a standard deviation of 10 in the Q-TWiST score. We acknowledge that the actual standard deviation of the Q-TWiST score could be quite a bit different here because the variance of the Q-TWiST score will depend on the joint distribution of the 5 restricted mean estimates, which will depend on the actual distributions, as well as on the utility weights for the different states.

Clinically Important Difference	Standard Deviation	N (per group)	Power
2.4	5	135	97
2.4	6	135	90
2.4	7	135	80
2.4	8	135	69
2.4	9	135	58
2.4	10	135	50
2.4	5	120	95
2.4	6	120	86
2.4	7	120	75
2.4	8	120	63
2.4	9	120	53
2.4	10	120	45

9.8.2 Analysis plan for PROs

Primary Q-TWiST Analysis. Due to the complexity of the current study (with the subsequent treatment after disease progression on the initial treatment), the basic 3-state Q-TWiST model is extended to a 5-state model in order to calculate the Q-TWiST score. For each initial treatment group, overall survival will be partitioned into five distinct clinical health states as listed below:

- TOX1: Toxicity with initial treatment (during step 1) is defined as the time spent with grade 3 or 4 toxicities prior to disease progression on the initial treatment. The start and end date for each adverse event will be captured. A day with multiple qualifying adverse events will only be counted once. For patients with severe toxicities reported in step 1 but no end date reported, TOX1 will be capped at the date of disease progression in step 1 or death without progression.

- TWiST1: Time without symptoms of disease progression or toxicity of initial treatment is defined as the number of days in step 1 prior to disease progression and with no grade 3 or 4 toxicities reported. Specifically, this is the time from study entry to disease progression on the initial treatment or death without progression, minus TOX1.
- TOX2: This toxicity period is defined as the time spent with grade 3 or 4 toxicities after disease progression on the initial treatment (in step 1) and prior to 2nd disease progression on the subsequent treatment (in step 2). The start and end date for each adverse event will be captured. A day with multiple qualifying adverse events will only be counted once. For patients with severe toxicities reported during this period but no end date reported, TOX2 will be capped at the date of disease progression on the subsequent treatment or death without progression.
- TWiST2: Time without symptoms of 2nd disease progression or toxicity of subsequent treatment is defined as the number of days after disease progression on the initial treatment and prior to the 2nd disease progression on the subsequent treatment and with no grade 3 or 4 toxicities experienced during this time period. Specifically, this is the time from 1st disease progression to 2nd disease progression or death without progression, minus TOX2.
- PROG: This progression health state is defined as the time from the last disease progression on the study to death from any cause.

The above health states are progressive, but it is not required for all patients to go through all the 5 states. For example, for patients without disease progression on the initial treatment, they will not enter TOX2, TWiST2, and PROG states.

The Q-TWiST score is obtained by summing the weighted clinical health state durations. The Q-TWiST score for each treatment arm will be calculated using the following formula:

$$Q-TWiST = (u_{TOX1} \times TOX1) + (u_{TWiST1} \times TWiST1) + (u_{TOX2} \times TOX2) + (u_{TWiST2} \times TWiST2) + (u_{PROG} \times PROG)$$

where u_{TOX1} , u_{TWiST1} , u_{TOX2} , u_{TWiST2} , u_{PROG} represent the average group utility weight for each health state for that arm; TOX1, TWiST1, TOX2, TWiST2, and PROG represent the mean duration of the health state of that arm.

In the Q-TWiST analysis, each health state is assigned a weight ranging from 0 (representing death) to 1 (indicating perfect health). These weights are called utility scores as well. For each patient, EQ-5D will be administered multiple times (at baseline, at each cycle while during the initial and subsequent treatment period, then every 3 months up to 2 years from study entry if patients are off protocol

treatment and not receiving non-protocol therapy, at end of treatment in each step (before and after crossover), and at dose modification) and its score will be used to derive the utility score. In this study, the utility score is conditional on the patient-reported health state on the 5 dimensions (mobility, self-care, usual activities, pain/discomfort, anxiety/depression) captured in EQ-5D. A number ranging from 1 to 5 will be assigned to each level in each of the 5 dimensions. A patient's health state thus can be labeled using a 5-number descriptor ranging from 11111 to 55555. A utility score corresponding to each possible descriptor elicited from general population samples (by country) was provided in the file "EQ-5D-5L_Crosswalk value sets" posted in the website of www.euroqol.org.⁴⁶ We are going to use the value set elicited from US subjects for our patients in this study. For instance, a health state with a descriptor of "11111" is given a utility score of 1.000, "12111" is assigned a utility value of 0.854, and "43333" is with a utility score of 0.573.

The average EQ-5D utility score for a patient's individual health state will be computed across all utility scores collected during that health state. For instance, EQ-5D scores for all visits during which a grade 3 or 4 adverse event is reported before the patient experiences disease progression on initial treatment will be averaged to form that patient's TOX1 utility score. All EQ-5D scores for visits without either grade 3 or 4 adverse events or disease progression on initial treatment will be averaged to form the patient's TWiST1 utility score. Similar definition and computation apply for TOX2 and TWiST2 with respect to the subsequent treatment. All EQ-5D scores for visits after last disease progression will be averaged to form that patient's PROG utility score. For each health state, the average group utility score is the mean of that health state within each treatment arm.

The restricted mean amount of time for each health state will be estimated using the Kaplan-Meier method, with time limit set at 2 years for computation of all restricted means. The duration of each health state is defined as follows:

- Mean duration of TWiST1 = mean PFS1 – mean TOX1,
- Mean duration of TWiST2 = mean PFS2 – mean TOX2,
- Mean duration of PROG = mean OS – mean PFS2,

where PFS1 is defined as the time from study entry to the first disease progression on the initial treatment. For patients alive without first disease progression, PFS1 will be censored at the date of last disease evaluation in step 1. PFS2 is defined as the time from study entry to the second disease progression on the subsequent treatment (in step 2). For patients enrolled into step 2, if they are alive without disease progression in step 2, PFS2 will be censored at the date of last disease evaluation in step 2. For patients not enrolled into step 2, PFS2 will be censored at the date of last disease evaluation in step 1. OS is defined as the time from study entry to death from any cause, censored at the date of last contact. TOX1 is defined as the days spent with grade 3 or 4 toxicities prior to disease progression on the

initial treatment (in step 1). For patients with severe toxicities reported in step 1 but no end date reported, TOX1 will be capped at the date of disease progression in step 1 or death without progression. TOX2 is defined as the number of days with grade 3 or 4 toxicities reported after the first disease progression on the initial treatment (in step 1) and prior to the second disease progression on the subsequent treatment (in step 2). For patients with severe toxicities reported during this period but no end date reported, TOX2 will be capped at the date of disease progression on the subsequent treatment or death without progression. For patients not receiving the subsequent treatment, TOX2 is counted as 0.

There are a couple of special notes for this expanded Q-TWiST analysis. If patients die during an early state and EQ-5D is not administered thereafter, the utility score in each of subsequent states will be defined as 0. If patients withdraw or lost to follow-up during an earlier state, the utility score in subsequent states will be assigned 0.. Finally, since Q-TWiST is being computed for 2 years in this study, once the duration of earlier states reach 2 years, the utility score collected in subsequent states will be used for these patients in the 2-year Q-TWiST analysis.

The mean amount of time for each health state and the average group utility scores will be summarized by initial treatment (i.e., arm A: ipilimumab + nivolumab (with subsequent dabrafenib + trametinib) vs. arm B: dabrafenib + trametinib (with subsequent ipilimumab + nivolumab)). The Q-TWiST subscore and the overall Q-TWiST score will then be reported by initial treatment. Differences between treatment groups in the mean Q-TWiST score (including the overall score and the subscore) will be calculated. For each score, a 95% confidence interval (CI) and two-sided P-value for testing the null hypothesis of no difference between treatment groups will be conducted using a Z-test (with normal approximation), with standard errors calculated by the bootstrap method. The bootstrap will be performed by repeated sampling, with replacement, from the sample of patients enrolled in this study, to obtain a new sample. The means for the new sample will be calculated using the same method as described above. This process will be repeated 1000 times. Based on the means obtained by the bootstrap method, the standard errors can be calculated.

Due to the multiple assessment timepoints for EQ-5D (at baseline, at each cycle while during the initial and subsequent treatment period, then every 3 months up to 2 years from study entry if patients are off protocol treatment and not receiving non-protocol therapy, at end of treatment in each step (before and after crossover), and at dose modification), we do not expect too many patients that reach a state but do not get any EQ-5D evaluation for the utility calculations. If this indeed occurs, it suggests that the reached state is rather short. For the primary Q-TWiST analysis, we assume these data will be missing at random then compute the average group utility weight for each health state based on patients with nonmissing data on the reached

states. If more than 20% of the cases have missing data, with respect to any reached health state, a sensitivity analysis will be performed with missing utility scores on a reached state being replaced by the average EQ-5D utility score from these patients' preceding health state. In case of discrepancies between the primary analysis and the sensitivity analysis, possible explanations will be discussed.

Secondary PRO Analysis. Overall function will be assessed (at baseline, weeks 6 (end of cycle 1), weeks 12 (end of cycle 2), and months 6 (disease stability)) while during the initial and subsequent treatment period (at 6-week, 12-week, months 6, 12, 18, and 24 from study entry (even off study treatment)) using PROMIS PROFILE-29. This instrument, consists of 7 short forms (Depression, Anxiety, Physical Function, Pain Interference, Fatigue, Sleep Disturbance, and Ability to Participate in Social Roles and Activities, with 4 items in each short form) together with one Pain Intensity item. Each item has five response options ranging in value from 1 to 5, except for the Pain Intensity item which has eleven response options ranging in value from 0 to 10. A raw score can be computed for each short form by summing the values of the response to each question within each domain.

The total raw score for each short form can then be converted into a standardized T-score with a mean of 50 and a standard deviation of 10. As to the Pain Intensity item, the raw response (0-10) can be used directly in data analyses.

Given differential attrition might exist in the two treatment groups and a high level of missing data is expected toward the end of the two-year PRO period with advanced melanoma patients (2-year OS rate expected to be 70% vs. 50% for arm A and arm B, respectively), a log-normal survival model will be implemented to adjust for potentially informatively censored data, using the expectation-maximization (EM) algorithm, as described in Schluchter (1992).⁴⁷ A log-normal survival model for analyzing longitudinal data (collected at baseline, 6-week, 12-week, months 6, 12, 18, and 24 from study entry) which incorporates the non-ignorable censoring mechanism will be fitted for each short form T-score and pain intensity, separately, to assess initial treatment effect (i.e., arm A: ipilimumab + nivolumab (with subsequent dabrafenib + trametinib) vs. arm B: dabrafenib + trametinib (with subsequent ipilimumab + nivolumab)) on each function.

To evaluate the effect of treatment sequence on patient function, each of the PROMIS short form T-score and pain intensity (with longitudinal data collected at baseline, 6-, 12-weeks, and 6-months after the initiation of treatment in each step) will be compared by treatment sequence for ipilimumab + nivolumab (arm A vs. D) and for dabrafenib + trametinib (arm B vs. C), using a log-normal survival model as described above.

PRO-CTCAE consisting of 17 symptoms (rash, headache, muscle pain, joint pain, decreased appetite, nausea, vomiting, constipation,

diarrhea, fatigue, cough, chills, itching, abdominal pain, shortness of breath, swelling, and increased sweating) will be administered multiple times (at baseline, at each subsequent cycle while during the initial and subsequent treatment period, at end of treatment in each step (before crossover and after crossover), and at dose modification).

PRO-CTCAE measures, if applicable, patient-reported presence (yes or no), frequency (never, rarely, occasionally, frequently, or almost constantly) and severity (none, mild, moderate, severe, very severe) on each of the specified symptoms. To evaluate the effect of treatment sequence on symptoms, summary statistics (frequency (N) and percentage (%)) will be reported with respect to presence, frequency and severity (if applicable) for each symptom by treatment sequence for ipilimumab + nivolumab (arm A vs. D), and for dabrafenib + trametinib (arm B vs. C) at baseline, 6-, 12-weeks, and 6-months after the initiation of the first treatment and the secondary treatment.

Rev. Add10 **10. Biological Sample Submissions**

Diagnostic material from previously collected tissue must be submitted for central diagnostic review and retention of a portion for defined immune biomarker assays and future undefined research studies such as PDL-1 and other bio-markers (per patient consent). Peripheral blood is to be submitted from consenting patients for defined laboratory research studies.

It is required that all samples submitted on this trial be entered and tracked using the ECOG-ACRIN Sample Tracking System (see Section [10.4](#)). An STS shipping manifest form is to be included with every submission.

All samples must be labeled clearly with the ECOG-ACRIN protocol number (EA6134), ECOG-ACRIN patient sequence number, patient's initials, date of collection and sample type.

